University of Arkansas for Medical Sciences (UAMS) Clinical Protocol

Study Title: Effects of 12 Weeks of Nutritional Therapy Interventions in Heart Failure

Principal Investigator: [name].
University of Arkansas for Medical Sciences
[name]
[name]
Office [contact]
Email: [contact]

Sub-Investigators: [name].
[name].
[name].
[name].
[name]
[name].
University of Arkansas for Medical Sciences
[name]
[name]

Study location: Donald W. Reynolds Institute on Aging @ UAMS
[name]
[name]

Support (Funding): NIH STTR grant to Essential Blends, LLC.; subcontract to UAMS

Table of Contents

Table of Events.....	4
1.0 Background and Rationale	5
2.0 Hypotheses	7
3.0 Study Design and Procedures	7
3.1 Study Visits	7
3.2 Subject Compliance	9
3.3 Subject Compensation.....	10
3.4 Randomization	10
3.5 Blinding.....	10
3.6 Study Products.....	11
3.7 Sample Storage	11
4.0 Study Population	12
4.1 Inclusion Criteria	12
4.2 Exclusion Criteria.....	12
5.0 Risks and Benefits	13
5.1 Blood, urine and fecal sampling:	13
5.2 DEXA scan:	13
5.3 Exercise testing (strength and functional):	14
5.4 Study supplements:.....	14
5.5 Confidentiality:.....	14
5.6 Oral isotope ingestion:	14
6.0 Data Handling and Recordkeeping.....	14
7.0 Data Analysis.....	15
7.1 Statistical Analysis plan	15
7.2 Significant Interaction Analysis Plan	15
7.3 Sample Size Calculation & Power Analysis	16
7.4 EAA mixture or placebo Effect	16
7.5 Time Effect.....	17
7.6 Urine analyses	17
7.7 Fecal analyses	17
7.8 Blood analyses.....	18

8.0 Ethical Considerations 18

9.0 Dissemination of Data..... 19

10.0 References 19

11.0 Appendices 21

 11.1 Study Product Information 21

Table of Events

Event	V.1	V.2	V.3	V.4	V.5	V.6	V.7	V.8	V.9	V.10	V.11	V.12	V.13	V.14
Informed Consent	x													
SLUMS	x													x
Medical History	x													
Meds used	x													
Ht & Wt.	x													
Temp & BP	x													
Blood sample ¹	x													
Ingest D3-cr.		x											x	
Phys. exam ²	(x)	(x)												
Collect urine for 3 days		x ³											x ³	
Fasting before visit		x												x
Blood sample ⁴		x												x
Urine sample		x												x
Stool sample ⁵		x												x
Strength & functional tests		x						x						x
Practice strength test	x													
SF-36 questionnaire		x						x						x
DEXA scan		x												x
Issue diet records		x						x					x	
Collect diet records			x						x					x
Dispense study product and diary		x	x	x	x	x	x	x	x	x	x	x	x	
Return study product and diary			x	x	x	x	x	x	x	x	x	x	x	x

¹ For criteria-related testing.² Can be done on visit 1 or 2.³ Between visits, at home. Calls will be made to remind subjects of the time for collection.⁴ For protocol endpoints.

⁵ If subjects unable to provide at this visit, they can take home a collection kit to return at next visit.

1.0 Background and Rationale

Heart failure develops when cardiac muscle becomes weakened and consequently is compromised in its ability to contract, relax, or both. Impaired heart function leads to reduced exercise capacity, which in turn leads to progressive muscle weakness and a vicious cycle of sedentary behavior, weight gain, and subsequent development of metabolic abnormalities and sarcopenia. Approximately 6-10% of individuals over the age of 65 suffer from heart failure (1). The risk of death is 35% in the first year after diagnosis, and decreases to about 10% per year thereafter (2). There are two principal forms of heart failure. Most commonly, heart failure has referred to reduced force of ejection (systolic heart failure). Heart failure may also result from an impaired ability of the heart to relax (diastolic heart failure) (3). Systolic heart failure is often accompanied with diastolic dysfunction (1-2). However, more often the contractile capacity of the heart is not affected, or only slightly impaired, and thus (unlike the case with systolic heart failure) the ejection fraction is usually preserved. This form of heart failure is termed heart failure with preserved ejection fraction (HFPEF), and is the predominant form of heart failure world-wide (4,5). Not only are there different types of heart failure, there is a wide range of potential causes of heart failure, including the natural process of aging (6). Regardless of the specific underlying cause or type of heart failure, there are common pathophysiological responses. Most prominently, impaired exercise capacity, shortness of breath, fatigue and muscle strength are hallmarks of heart failure that lead to decreased physical function, and ultimately sedentary behavior and development of insulin resistance (2). Heart failure is also associated with fluid retention and even edema of the intestinal wall which resultant malabsorption of nutrients (7). Poor health of the intestinal mucosa in heart failure might potentially also influence the gut microbiome. Some long-term consequences of reduced exercise tolerance and malabsorption in long-standing heart failure are loss of muscle mass and the development of cardiac cachexia (7). These responses not only contribute to morbidity and mortality and financial strain on the health care system, but to decreased health-related quality of life.

Treatment of the underlying cause of heart failure would be optimal. Indeed, pharmacological treatment of heart failure predominantly targets the improvement of cardiac performance.

Heart failure may be treated with varying degrees of success with a variety of drugs, including angiotensin-converting (ACE-inhibitors, angiotensin II, beta blockers, diuretics, digoxin, nitrates and others). However, treating systolic heart failure pharmacologically may be quite complex in the elderly. More than 50% of individuals over age 65 with heart failure have at least four co-morbidities (8), and these may complicate therapy of heart failure. Adverse responses to pharmacological therapy are not uncommon, including the fact that both ACE inhibitors and beta blockers can adversely affect muscle function (9). Further, HFPEF is becoming more widely recognized, and to date, despite the expenditure of millions of dollars and years of time and effort, not one large-scale clinical study of a single drug therapy has demonstrated a substantial beneficial outcome. This disappointing reality may reflect the difficulty of treating a syndrome with diverse causes, interacting complex pathogenesis, and multiple co-morbidities with an entirely drug-oriented approach. Reduced exercise capacity is a prominent clinical feature of heart failure. This leads to progressive muscle weakness and a vicious cycle of sedentary behavior, weight gain, and subsequent development of metabolic abnormalities and sarcopenia.

In this study we will perform a randomized clinical trial of a commercially produced nutritional supplement (EAA mixture Essential Blends, Fairbanks, AK) as compared to a placebo in order to determine effects on physical function and health-related quality of life. Subjects will ingest either the EAA mixture product or placebo every day for 12 consecutive weeks. Outcomes will be determined by comparing the results of physical and functional tests from weeks -1 to 6 and 12.

In a pilot study 18 overweight/obese subjects with heart failure (all exceeded 40% body fat) were studied. Nine subjects received 12 weeks of dietary supplementation with 20 g of whey protein consumed daily, while the other nine were controls. Consistent with the acute data showing a limited stimulation of muscle protein synthesis with dietary amino acids in the profile of whey protein in even healthy elderly (i.e., anabolic resistance, Figure 1), supplementation with whey protein failed to improve functional performance. The lack of a demonstrable effect of whey is consistent with the diminished responsiveness to the stimulation of muscle protein synthesis by whey protein in heart failure (10). In contrast, a 2016 UAMS pilot study found that the EAA mixture is better at overcoming anabolic resistance than Ensure Heart Health (see below).

[figure not shown]

Figure 5. Average rates of Protein synthesis, breakdown and net balance between synthesis and breakdown after consumption of Ensure Heart or UpBeat. **significantly different from fasted state ($p < 0.005$); ***significantly different from fasted state ($p < 0.0005$); ## significantly different between treatments ($p < 0.005$).

2.0 Hypotheses

1. We propose that 12 weeks of regular consumption of EAA mixture will improve physical function in individuals with heart failure as compared to placebo.
2. We propose that regular consumption of EAA mixture will improve health-related quality of life as compared to placebo.

3.0 Study Design and Procedures

This is a randomized, double blind, prospective study examining the effects of 12 weeks' ingestion of either EAA mixture or placebo on physical function. We will also examine several blood parameters and fecal microbiome in both groups of subjects (see section 5.1). Up to 80 subjects ages 60 to 89 will be enrolled to obtain 60 completers (30 per group).

3.1 Study Visits

Visit 1: subjects will come to the UAMS IOA 3rd floor for informed consent discussion. Once consent is obtained, study staff will administer and score the SLUMS test for dementia. If subjects score >20 , subsequent study procedures will be performed. A medical history and list of current medications will be obtained (printed from Epic if they are a UAMS patient). Subject height, weight, body temperature and blood pressure will be measured. A blood sample will be drawn (approx. 15 mL) for criteria-related tests if recent results are not available from their medical record. A brief training session will take place where subjects will be introduced to the

isokinetic dynamometer (Cybex) machine and how it is used at the testing visits. They will undergo a practice test on one leg.

A physical exam will be performed at this visit or at visit 2. Based upon the results of the screening blood sample, visit 2 will be scheduled.

Visit 2: Subjects must come to this visit having fasted overnight. They will be asked about any adverse events since last visit. A fasting blood sample (~30 mL) will be drawn to determine baseline values (tests listed below), and a snack will be provided and coffee offered. A urine sample will be collected for dipstick proteinuria. Subjects will be asked to provide a stool sample, but if unable at this visit, they can take home a sample collection kit to use. They will be instructed to collect the stool sample at home on the day of Visit 2 or at UAMS. Subjects will be provided with a drink containing 30mg of a stable isotope of creatine (D-3, Cambridge Isotopes Laboratory, Tewksbury, MA) dissolved in water. They will be asked to collect 3 separate urine samples over the next 72 hours at approximately 24-hour intervals, place them into their freezer, and return them to UAMS at their next visit.

If not performed at visit 1, the physical exam will be performed at this visit. Randomization will be performed as mentioned below. The following assessments will be performed: functional (6-minute walk distance), SF-36 health questionnaire, a whole-body DEXA scan for lean mass measurement, strength (Cybex testing of maximal voluntary contraction of each leg; bilateral hand grip strength). Subjects will be provided with forms and training for recording their dietary intake over a 3-day period during the next week. Study staff will dispense approximately 10 days' worth of study product and a consumption diary for subjects to complete after ingesting each dose. Future visits will be scheduled.

Visits 3-7: Subjects will come to the IOA weekly to return their urine samples, empty supplement containers and consumption diary. They will be asked about any adverse events since last visit. Study staff will dispense more study product and a consumption diary.

Visit 8: Subjects will be asked about any adverse events since last visit. They will return their empty supplement containers and consumption diary. In no particular order, the following assessments will be performed: strength (Cybex testing of maximal voluntary contraction of

each leg; bilateral hand grip strength), functional (6-minute walk distance), SF-36 health questionnaire. Study staff will dispense more study product, a consumption diary, and another 3-day diet diary.

Visits 9-12: Subjects will come to the IOA weekly to return their empty supplement containers and consumption diary. They will be asked about any adverse events since last visit. Study staff will dispense more study product and a consumption diary.

Visit 13: Subjects will come to the IOA to return their empty supplement containers and consumption diary. They will be asked about any adverse events since last visit. Study staff will dispense more study product and a consumption diary. Subjects will be provided with a drink containing 30mg of a stable isotope of creatine (D-3, Cambridge Isotopes Laboratory, Tewksbury, MA). They will be asked to collect 3 separate urine samples over the next 48 hours at approximately 24-hour intervals and return them to UAMS at their next visit. Subjects will be issued a stool sample collection kit to use just prior to visit 14 and another 3-day diet diary.

Visit 14: Subjects must come to this visit having fasted overnight. They will be asked about any adverse events since last visit. They will return their diet records, empty supplement containers, any full supplement containers, their stool sample, and their consumption diary. Study staff will administer and score the SLUMS test for dementia. A fasting blood sample (~30 mL) will be drawn. After the blood sample is drawn, subjects will be offered a meal and beverages. A urine sample will be collected for dipstick proteinuria.

The following assessments will be performed: functional (6-minute walk distance), SF-36 health questionnaire, a whole-body DEXA scan for lean mass measurement, strength (Cybex testing of maximal voluntary contraction of each leg; bilateral hand grip strength). At the end of this visit, subject will have no further study visits.

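### When the physical exam is deferred to Visit 2, the Visit 1 practice strength test needs no prior medical clearance

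*Combined protocol and SAP*

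**What the plan says.** Under Section 3.1, Visit 1 opens with consent and the SLUMS test. If the score is above 20, "subsequent study procedures will be performed". History, medications, height, weight, temperature and blood pressure come next, with a blood draw if recent results are not on file. Then "A brief training session will take place" on the dynamometer, and "They will undergo a practice test on one leg". The Table of Events lists "Practice strength test" at Visit 1 only.

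The exam is not tied to that visit. Section 3.1 says "A physical exam will be performed at this visit or at visit 2", footnote 2 of the Table of Events says "Can be done on visit 1 or 2", and the Visit 2 text adds "If not performed at visit 1, the physical exam will be performed at this visit".

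The last item of Section 4.2 excludes anyone the study physician judges medically unstable, without saying when that judgement is made. Section 5.3 has staff stay close during exercise tests and stop them for tiredness, breathlessness or any safety concern.

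**The concern.** The practice has a fixed visit and the exam does not. Whenever the exam is deferred, the subject's first strength effort comes before it. That would matter little if some other medical check had to come first, but none is required.

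The population makes the order worth settling. Subjects are 60 to 89 years old with NYHA II or III symptoms. Section 4.1 accepts prescribed diuretics or reported breathlessness on exertion as evidence of heart failure. Section 4.2 excludes recent infarction, unstable angina, significant valve disease and certain cardiomyopathies, while the Table of Events lists no ECG or echocardiogram. Applying those exclusions therefore rests on history, records, the exam and a physician's judgement.

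This is a point of subject safety only. It does not touch the hypotheses, the endpoints, the alpha level or the power calculation.

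**Working it through.** The plan gives no figure on this point, so there is nothing to reproduce. The check sets the relevant provisions side by side and then counts the exposure.

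**Is any medical clearance required before the practice?**

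| Provision | Where | Required before the practice? |
|---|---|---|
| SLUMS score above 20 | 3.1, Visit 1 | Yes, but it is a cognitive screen |
| History, medications, blood pressure | 3.1, Visit 1 | Listed first, but no physician review or go/no-go rule is attached |
| Screening bloods | 3.1, Visit 1 | No; the results govern the scheduling of Visit 2 |
| Physical exam | 3.1; Table of Events, footnote 2 | No; Visit 1 or Visit 2 |
| Study-physician judgement of instability | 4.2 | Not stated; no time point |
| Staff presence and stopping rules | 5.3 | No; they act during a test and do not decide who starts |
| PI safety monitoring | 6.0 | No; a general duty |
| PI referral from clinic | 4.0 | No; one of two recruitment routes, and past subjects called by study staff have no clinic referral step |

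No row is a required medical clearance. The instability criterion exists, so what is missing is its timing. It may be applied before the practice, but nothing makes that necessary.

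**What does a deferred exam still precede?** The Visit 2 text lists it ahead of randomization, maximal leg contraction, grip strength and the 6-minute walk. Maximal voluntary contraction is named only at Visits 2, 8 and 14. The exposure is therefore limited to the Visit 1 practice.

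**How many practices?** Section 3.0 gives the ceiling: "Up to 80 subjects ages 60 to 89 will be enrolled to obtain 60 completers". Each subject does one practice. Let d be the share of exams deferred to Visit 2. The documents do not give d, so the whole range is shown as an assumption:

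Practices with no required prior exam or physician judgement = 80 × d

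- d = 0: 80 × 0 = 0
- d = 0.25: 80 × 0.25 = 20
- d = 0.50: 80 × 0.50 = 40
- d = 1.00: 80 × 1.00 = 80

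Under the proposed rule the count is 0 at every d, by construction. The sum treats everyone who reaches the practice as enrolled; subjects who fail screening afterwards would add to it.

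**The case against.** The strongest reply is about weight. The practice is a short familiarisation on one leg with no stated maximal effort. The effects Section 5.3 names are soreness and fatigue, with dizziness and falls as the reason staff stay close. History, medications and blood pressure, which bear on the cardiac exclusions, are already listed before the practice. No eligibility criterion is expressly defined by an exam finding, so the documents do not show whom the exam would catch that the history would miss. Most Section 4.2 criteria carry no visit, so an untimed criterion is this protocol's usual style. The 0-to-80 range spans every possibility. The remedy needs a physician at Visit 1 whenever the exam is deferred, and it does not wait for pending bloods, so someone with low hemoglobin or low eGFR could still practise.

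Much of this stands. The risk is modest, the count bounds exposure and says nothing about harm, and the remedy secures a medical judgement without completing eligibility. It does not remove the gap. Collecting a history is not the same as having a physician act on it, and stopping rules apply only once a subject has begun. If a study physician already makes this judgement first, writing it down costs almost nothing; if not, the step is missing.

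**Conclusion.** The concern holds. As written, a subject whose exam is deferred can do the Visit 1 practice with neither an exam nor a study-physician judgement of stability required first. The size is 0 to 80 practices, depending on a deferral share that the documents do not give, with one practice per subject and up to 80 enrolled. No event rate is given and none is assumed.

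Confidence in the reading of the text is high. The importance is limited: this is a narrow sequencing gap with modest remaining risk. It should be corrected because the remedy is small and uses information already collected.

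**What to change.** Add one ordering rule to Section 3.1, Visit 1, and repeat it in footnote 2 of the Table of Events. Suggested wording:

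*The practice strength test is done only after either the physical exam or a documented study-physician review of the Visit 1 history, medications, vital signs and any laboratory results on file against Section 4.2. The exam may still be completed at Visit 2 when that review has been done.*

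This keeps the practice at Visit 1, away from the day of baseline strength testing, and keeps the option of a Visit 2 exam. It does not require waiting for pending bloods.

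The cost is one sentence in each place, a short physician note for each deferred exam, and some loss of scheduling flexibility, because a study physician must be available to review the record before the practice. No visit, test or measurement is added.

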5.0 Risks and Benefits

There are no direct benefits for the subjects apart from the possibility getting knowledge of their own results of the assessments and blood tests. Expected risks associated with this protocol are described in detail below. All experimental procedures will be performed by appropriately trained and credentialed personnel.

5.1 Blood, urine and fecal sampling:

The total amount of blood taken will be approximately 100 mL. Subjects will have no noticeable effects. The risks of collecting blood samples include pain, bruising and bleeding.

Urine samples will be tested using commercial dipsticks for proteinuria during visits 2 and 14.

Urine collected between visits 1-2 and 13-14 will be analyzed in the PI's lab for the isotope-labelled creatinine to determine skeletal muscle mass (14). There is no risk of collecting voided urine. Fecal samples will be collected at visits 2 and 14. There are no risks associated with collecting fecal samples.

5.2 DEXA scan:

The DEXA scan exposes subjects to approximately ½ of the radiation of one chest x-ray. They will undergo 2 DEXA scans in total.

5.3 Exercise testing (strength and functional):

Subjects may become sore or fatigued during or after the exercise tests. Study staff will remain close to subjects for safety, in the case of dizziness or potential falls. Tests will be paused or stopped if the participant is tired or short of breath. Tests will also be stopped if, for any reason, there is concern about the subject's safety. During the 6-minute walk test, subjects will wear a portable oxygen saturation monitor to allow study staff to observe for desaturation.

5.4 Study supplements:

There are potential allergens in the placebo: milk and soy. All components of EAA mixture (Table 4) are classified as Generally Regarded as Safe (GRAS) by the FDA. They will be provided by PrinovaUSA, which has all necessary certifications for safe production of dietary supplements.

5.5 Confidentiality:

A potential risk to study participants is the potential for loss of confidentiality. Measures to protect the confidentiality of study participants will be implemented as described in the Data Handling and Recordkeeping section below.

5.6 Oral isotope ingestion:

There are no known risks to ingesting 30mg of stable isotope-labelled creatine.

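### Section 3.1 gives conflicting collection windows and home-storage instructions for the D3-creatine muscle-mass measurement at baseline and at the end of treatment

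*Combined protocol and SAP*

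**What the plan says.** The tracer is given twice, 30 mg each time, at Visit 2 and at Visit 13. Each time the subject collects three urine samples.

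- Section 3.1, Visit 2: "They will be asked to collect 3 separate urine samples over the next 72 hours at approximately 24-hour intervals". Subjects are then to "place them into their freezer, and return them to UAMS at their next visit".
- Section 3.1, Visit 13: "They will be asked to collect 3 separate urine samples over the next 48 hours", again about 24 hours apart, and bring them back at the next visit. No home storage is mentioned.
- Table of Events: "Collect urine for 3 days", marked at both visits, with the footnote "Between visits, at home. Calls will be made to remind subjects of the time for collection".
- Section 5.1: "Urine collected between visits 1-2 and 13-14 will be analyzed", the purpose being to determine skeletal muscle mass.
- Section 7.6 sends three containers home, to be used after the tracer is taken, but gives no times.
- Section 3.7 sets a freezer temperature for urine, but only after the first processing step, so it does not reach the period at home.

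**The concern.** The same measurement, with the same tracer dose and number of samples, carries two different instructions before and after treatment. Nothing in the design explains the difference. Subjects collect at home, so what they are told decides when the samples are taken and how they are kept.

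These are the only two muscle-mass determinations by this method. If sampling time or storage affects the result, that effect cannot be separated from a true change between baseline and the end. A baseline value obtained under different conditions may also be a less useful covariate in the Section 7.1 model. Section 5.1 adds a further conflict: urine collected between Visits 1 and 2 precedes the first tracer drink and could not contain its label.

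**Working it through.** **1. The sources side by side**

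| Source | Baseline collection | Final collection |
|---|---|---|
| Section 3.1 | 72 h, about 24 h apart, home freezer | 48 h, about 24 h apart, storage not mentioned |
| Table of Events | 3 days, from Visit 2 | 3 days, from Visit 13 |
| Section 5.1 | between Visits 1 and 2 (before tracer) | between Visits 13 and 14 |
| Section 7.6 | after the tracer, times not given | after the tracer, times not given |

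The Table of Events agrees with the Visit 2 text and conflicts with the Visit 13 text. Sections 7.6 and 3.7 settle neither the window nor the home storage.

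**2. Does the stated spacing fit the stated window?**

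Let the first sample be taken *t* hours after the drink and let the spacing be *d* hours. The third sample falls at *t* + 2*d*, which must not exceed the window *W*.

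- Visit 2: *W* = 72, *d* = 24, so *t* ≤ 72 − 48 = 24. Using the whole window gives 24, 48 and 72 h.
- Visit 13: *W* = 48, *d* = 24, so *t* ≤ 48 − 48 = 0. Three samples fit only at 0, 24 and 48 h, and the first of these is not a post-dose sample.
- Visit 13 with the window divided evenly: *d* = 48/3 = 16, giving 16, 32 and 48 h, which departs from the stated spacing by 8 h.
- Visit 13 with some slack, for example *d* = 22: *t* ≤ 48 − 44 = 4, giving 4, 26 and 48 h.

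**3. Overlap with a baseline schedule of 24, 48 and 72 h**

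- 0, 24, 48 h: two of three times shared.
- 16, 32, 48 h: one of three shared.
- 4, 26, 48 h: one shared exactly and one approximately.
- If 48 hours was meant as the time from first to last sample, 24, 48 and 72 h fits both visits and all three are shared.

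On every literal reading the 72 h baseline sample has no counterpart at the end.

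**4. Which analysis is exposed?**

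Suppose the final collection shifts measured muscle mass by an amount δ, additive and equal in both arms.

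- Between arms at the final visit: (final mean, EAA + δ) − (final mean, placebo + δ). The δ cancels.
- Change within a group: (final mean + δ) − baseline mean. The δ remains.

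Section 7.1 uses baseline as a covariate. Section 7.2 compares arms at the midpoint and final times, and Section 7.5 builds its time effect on the midpoint-to-final difference. D3-creatine muscle mass has no midpoint value, so that time effect cannot be run on it. The exposed quantity is therefore any baseline-to-final change that may be reported.

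**5. Size**

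The documents give no relation between estimated muscle mass and either sampling time or home storage, so δ cannot be calculated.

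**The case against.** The strongest reply is that this is a drafting slip. The Table of Events gives 3 days and reminder calls at both visits, and the reference to Visits 1–2 in Section 5.1 looks like another slip. Three samples 24 hours apart do span 48 hours, so the author may have meant that span. This is plausible, and it means a mismatch in actual conduct is not shown. It does not remove the conflict: the Visit 13 sentence has the same form as the Visit 2 sentence, and staff or subjects could follow it literally.

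The measure is also of limited weight. It is not in the Section 2.0 hypotheses, the endpoints powered in Section 7.4 or the secondary endpoints named in Section 7.3, and lean mass is measured separately by DEXA at Visits 2 and 14. That stands, and it limits the importance of the point.

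Three stronger readings are tempting and are not supported:

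- A reader might infer that the treatment comparison is biased. Both randomised arms receive the same instructions, so a common shift cancels.
- A reader might infer that the planned within-group time test is contaminated. As Section 7.5 defines it, that test needs a midpoint value, which this measure lacks.
- A reader might infer that final samples are taken at 0, 24 and 48 h and left unfrozen. That schedule is only one reading, and it sits poorly with home collection after the tracer. Freezing at Visit 13 is omitted, not forbidden.

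Nor can a loss of precision from discarding unmatched samples be given a figure, because the documents do not say how the three samples are combined.

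**Conclusion.** The point holds as an internal contradiction that should be corrected. The written instructions do not give comparable baseline and final collections: 72 against 48 hours, and a freezer instruction at one visit only. Read literally, at most two of the three sample times match, taking baseline as 24, 48 and 72 h.

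The consequence is conditional. If the text is followed as written, and if sampling time or storage affects the result, a baseline-to-final change in muscle mass is confounded with them and the baseline covariate may lose some of its value. Under a shift common to both arms, the randomised comparison is not systematically biased. The sample size is unaffected. The wording conflict is certain; whether conduct differed is unknown.

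**What to change.** Reconcile the Table of Events, the Visit 2 and Visit 13 text in Section 3.1, Section 5.1 and Section 7.6 to one collection window, one set of post-dose times and one home-storage instruction, used identically at both time points. The documents do not settle which window is intended, so the sponsor must decide. Record the actual time of each drink and each urine sample. Visit 14's list of returned items should also name the urine samples, which Visit 13 says come back then.

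For subjects already studied, check any recorded times. If they show a mismatch, base any reported change in muscle mass on samples at matched post-dose times.

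The cost is a text correction and a revised subject instruction sheet, plus the recording of times. No samples are added.
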